#### Debriefing questionnaire

We will finally explore whether the restaurants menus are valid and the extent to which participants reported using kcal information when making food choices. Responses to the debriefing questionnaire will be analysed:

- We will describe the responses to each item (mean, SD, % agree [5, 6, 7], % disagree [1, 2, 3]) in the overall sample to characterise *validity of menu design, validity of food offer, kcal influence*.
- Three linear mixed models will be used to test the effect of *labelling, availability, familiarity* and *highest educational level* on the three dimensions of the debriefing questionnaire (a) *validity of menu design*, (b) *validity of food offer*, and (c) *kcal influence* to investigate whether the responses differ across experimental conditions and SES.

To account for multiple testing the alpha level for secondary analyses will be set at  $p = 0.01$ .

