### 3. EXPERIMENTAL DESIGN

Participants will be enrolled in an online survey and make hypothetical menu choices. Participants will be randomized into a mixed-design experiment with 2x2 between-subjects conditions with factors of kcal labelling (absent vs. present) and availability (baseline availability of main dishes with  $\leq 600$ kcals vs. higher availability of main dishes with  $\leq 600$ kcals) and 6 repeated measures (3 familiar and 3 unfamiliar menus).

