##### **From the debriefing questionnaire:**

- **Validity of menu design** (item 2)
- **Validity of food offer** (items 4 and 5)
- **Kcal influence** (item 3)

Answers to all the items will be coded as: 1 = Strongly disagree; 2 = Disagree; 3 = Slightly disagree; 4 = Neither agree or disagree; 5 = Slightly agree; 6 = Agree; 7 = Strongly agree.

Internal dimension consistency of the items measuring *validity of food offer (for each cuisine)* will be assessed by calculating McDonald's  $\omega$  for each, which is an alternative to Cronbach's  $\alpha$  when the total test scores are normally distributed (i.e., all items are normally distributed) [32]. If adequate consistency is reached ( $\omega \geq 0.7$ ), *validity of food offer (for each cuisine)* score will be calculated as the mean of the two items constituting the dimension. In the case where internal consistency is not acceptable, we will run analyses separately on individual items.

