#### **Cuisine familiarity**

- Familiarity condition: Binary variable based on the experimental design: 0 for unfamiliar cuisines and 1 for familiar cuisines
- Familiarity score: Ordinal variable based participants answer for each cuisine to the question "Have you ever tried [6 cuisines]?" coded as 1: Never tried; 2: Not in the last year; 3: Less than once per month; 4: 1-3 times per month; 5: 1-2 times per week; 6: 3 times per week or more

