### 7.4. Main analyses

The measure of SES used in our primary analysis will be the *highest educational qualification* (categorical variable: *lower vs. higher*) because previous research showed that people with college education were more likely to use kcal labels at restaurants [37]. The measure of health motivation will be the response to the first item from the Single-item Food choice Questionnaire: “It is important to me that the food I eat on a typical day is healthy”, i.e., importance of healthiness.

First, we will examine whether our manipulation of familiarity is valid by examining the proportion of participants that are familiar / unfamiliar with each cuisine menu type (i.e. we expect >75% of participants to be familiar with our chosen ‘familiar’ cuisines and <25% of participants to be familiar with our ‘unfamiliar’ cuisines). We will also report the mean and SD of the *familiarity score* for each cuisine.

A linear mixed model will be used to test the effect of *labelling* (categorical, between-subject), *availability* (categorical, between-subject), *highest educational qualification* (categorical, between-subject), *familiarity* (categorical, within-subject) and *labelling\*highest educational qualification*, *availability\*highest educational qualification*, *labelling\*familiarity*, *availability\*familiarity*, interactions on *energy of the main* for the six dining out scenario. A random effect of participant will be added by using an unstructured covariance structure to account for correlation between repeated ordering by the same participant.

If any interactions with *familiarity* are significant, analysis will be stratified by *familiarity* and two linear mixed models will be fitted to examine the effect of *labelling*, *availability*, *highest educational qualification* and *labelling\*highest educational qualification*, *availability\* highest educational qualification* interactions on *energy of the main* for familiar and unfamiliar cuisines with participant effect as random to account for correlation between repeated ordering by the same participant for familiar and unfamiliar cuisines.

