### Questionnaire:

**1. There was an acceptable number of food items on the menus.**

						
Strongly disagree	Disagree	Slightly disagree	Neither agree or disagree	Slightly agree	Agree	Strongly agree

**2. The food choices I made for each dining out scenario were influenced by how many calories I thought were in the food options available.**

						
Strongly disagree	Disagree	Slightly disagree	Neither agree or disagree	Slightly agree	Agree	Strongly agree

**3. The food items available in the menus are common in [...] style restaurants.**

	Strongly disagree	Disagree	Slightly disagree	Neither agree or disagree	Slightly agree	Agree	Strongly agree
American							
Mexican							
Italian							
Lebanese							
Peruvian							
Moroccan							

**4. The food items I picked for my meal in the [...] style restaurant would be something that I would normally order in the real world.**

	Strongly disagree	Disagree	Slightly disagree	Neither agree or disagree	Slightly agree	Agree	Strongly agree
American							

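### Two of the three debriefing models cannot estimate the planned familiarity effect, because menu design and kcal influence are each answered once for all six menus

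*Combined protocol and SAP*

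**What the plan says.** Section 7.5, under Debriefing questionnaire, specifies the models: "Three linear mixed models will be used to test the effect of *labelling, availability, familiarity* and *highest educational level* on the three dimensions". The three dimensions are validity of menu design, validity of food offer and kcal influence. The secondary alpha is 0.01.

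Section 7.2 defines the familiarity condition as "Binary variable based on the experimental design: 0 for unfamiliar cuisines and 1 for familiar cuisines". The main model in Section 7.4 treats it as a within-subject factor. Section 3 describes the design as having "6 repeated measures (3 familiar and 3 unfamiliar menus", so each participant contributes to both levels.

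Section 7.2 also assigns questionnaire items to the dimensions: "Validity of menu design (item 2") for the first and "Kcal influence (item 3") for calorie influence, with items 4 and 5 for food offer. Only food offer is described there as scored per cuisine.

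Appendix J opens its numbered statements with "There was an acceptable number of food items on the menus", followed as item 2 by the calorie statement, which begins "The food choices I made for each dining out scenario were influenced by how many calories I thought". Each of these has one seven-point scale. Items 3 and 4 are grids with a row for each of the six cuisines. Item 5 asks which cuisines the participant has tried and how often.

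**The concern.** A within-participant effect can be estimated only if the outcome is recorded at both levels of the factor. A single rating covering all six menus contains no familiar-versus-unfamiliar difference. Section 7.5 nevertheless promises a familiarity test on all three dimensions.

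At stake is whether a pre-specified test can be run at all. An analyst following Section 7.5 would meet an aliased familiarity term or a degenerate variance estimate in two models and would have to improvise. For kcal influence there is also lost information: the single answer cannot show whether self-reported attention to calories differed between familiar and unfamiliar menus, which is what a familiarity term in that model would be for.

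Separately, the item numbers in Section 7.2 do not lead to the intended statements in Appendix J.

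**Working it through.** The documents give no power or sample-size figure for the debriefing models, so there is nothing to reproduce. The check concerns estimability and cross-references.

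**Step 1. Match dimensions to items by content.**

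| Dimension | Number in Section 7.2 | Matching item in Appendix J | Responses per participant |
|---|---|---|---|
| Menu design | 2 | 1 | 1 |
| Kcal influence | 3 | 2 | 1 |
| Food offer | 4 and 5 | 3 and 4 | 6 per item |

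Two of the three outcomes have one response per participant. Every item number is shifted by one in the same direction.

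**Step 2. Outcome answered once.** The fixed-effect columns are intercept, labelling, availability, familiarity and education, five in all. Each participant sees menus coded 1, 1, 1, 0, 0, 0, so the only familiarity value that can attach to a single answer is their mean, 3/6 = 0.5, for everyone. That column equals 0.5 times the intercept. The rank was checked with 1,000 participants (the analysed sample in Section 7.6), simulating labelling, availability and education as binary variables:

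- with familiarity: 5 columns, rank 4, so familiarity is not estimable;
- without familiarity: 4 columns, rank 4, so the other effects are estimable.

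**Step 3. Participant effect.** With one response per participant, Var(y) = σ²(participant) + σ²(residual). Only the sum is identified, so the mixed model has nothing to separate.

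**Step 4. Outcome answered per cuisine.** With six rows per participant and familiarity coded by menu, the matrix has 5 columns and rank 5. The food-offer model can therefore estimate familiarity, and the repeated rows support a participant effect.

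**Step 5. Could the single answer be copied to six rows?** If participant i's answer y(i) is repeated, the familiar mean minus the unfamiliar mean is 3y(i)/3 − 3y(i)/3 = 0 for every participant. The simulated coefficient was 0 to rounding (about 1e-15) and the within-participant variance was exactly 0. This gives no test.

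**Step 6. Does the familiarity score repair it?** Section 7.2 also defines a participant-reported score from 1 to 6. It too is recorded per cuisine, Section 7.5 gives no rule for reducing it to one value per person, and a reduced score would answer a between-person question instead of the menu contrast. It does not rescue the models as written.

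**The case against.** The strongest reply is that little depends on this, and most of it stands. Section 7.5 presents these analyses as exploratory and states their purpose as comparing responses across experimental conditions and SES. Labelling, availability and education remain estimable for every dimension.

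A reader might infer that the secondary objective on familiarity is compromised. The documents do not support that. Section 2 gives that objective its own outcome, energy ordered from familiar and unfamiliar cuisines, and Section 7.4 tests labelling by familiarity on energy of the main. Neither depends on the debriefing item. That item also asks about calories the participant believed were present, so it does not isolate use of the labels.

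A reader might also infer that the condition effects would gain false precision from copied rows. Nothing in the plan says answers will be copied, and the planned class is a mixed model. In a simulation of 1,000 participants with an assumed SD of 1.5, the labelling standard error was 0.0944 with one row each and still 0.0944 with six copied rows and a participant effect. It fell to 0.0385 (0.0944/√6) only when that effect was left out.

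Finally, a reader might infer from the numbering that food offer would average a rating with a tick box. That is implausible. Section 7.2 names the dimensions, describes food offer as two items scored per cuisine on the agreement scale, and defines the ever-tried question separately as the familiarity score. The uniform shift would fit if the unnumbered aim-guessing question had been counted as item 1. Moreover, the count of two affected models rests on matching by content. Under the literal numbers, kcal influence would be item 3, a per-cuisine grid, and only menu design would be a once-only outcome. The two harms cannot be added together.

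None of this makes the familiarity term estimable for a once-only item.

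**Conclusion.** The point holds in a limited form. With items matched by content, the familiarity effect and the random participant effect cannot be estimated in two of the three debriefing models, menu design and kcal influence. Food offer supports both. This rests on Appendix J being the instrument used and on familiarity meaning the menu-level design factor, as in Sections 7.2 and 7.4. The item references in Section 7.2 are a uniform numbering slip that the wording allows one to correct.

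The reach is small: exploratory secondary analyses at alpha 0.01, with no effect on the primary analysis or on the familiarity hypothesis for energy ordered. It is still worth correcting, because a stated test cannot be run as written.

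**What to change.** 1. **Kcal influence.** Ask the item once per cuisine, in the same six-row grid as Appendix J items 3 and 4, and keep familiarity and the participant effect in its model. The cost is 6 − 1 = 5 extra responses per participant, after the meal choices have been made. If the item stays single, or the survey has already been fielded, remove familiarity and the participant effect and fit an ordinary linear model on labelling, availability and education with one row per participant. That costs only a change of wording, but no familiarity comparison is then possible for this item.
2. **Menu design.** Use the same one-row linear model without familiarity. Section 5.1 gives every scenario the same number of mains, sides and desserts, so a per-cuisine version of an item about the number of dishes would add little.
3. **Food offer.** Keep the mixed model with familiarity, and state the random participant effect explicitly in Section 7.5.
4. **Section 7.2.** Correct the references to menu design = item 1, kcal influence = item 2, food offer = items 3 and 4.

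A labelling-by-familiarity term for kcal influence would be a new question and is not needed to repair the defect.

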## 2. OBJECTIVES, OUTCOMES MEASURES AND HYPOTHESES

OBJECTIVES	OUTCOME MEASURES	HYPOTHESES
Primary objective  To examine the effect that an information-based intervention (energy labelling)	Energy (kcal) of the ordered meal.	An increased availability of lower energy menu options will result in a decrease in total

and a structural intervention (increased availability of lower kcals options) have on kcals ordered in a hypothetical meal ordering task among participants of lower and higher SES.
		
energy ordered among both participants of lower and higher SES. However, energy labelling may exert a stronger effect on energy ordered among participants of higher vs. lower SES.

Secondary objectives
 
To examine the reasons why the effects that energy labelling have on kcals ordered may vary based on a participants' SES.
 
To examine the effect of labelling on familiar and unfamiliar cuisines menus.
	
Health motivation in food choices (questionnaire score).
 
Energy (kcal) of the ordered meals for familiar and unfamiliar cuisines.
	
The participants of higher SES will be more motivated by health in their food choices than participants of lower SES, which will mediate the relationship between SES and the effect of energy labelling on the total energy ordered.
 
Energy labelling will have a greater effect for unfamiliar compared to familiar cuisines.

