### 7.5. Secondary analyses

#### Moderated mediation analysis of health motivation

[figure not shown]
If the main analyses suggest that *highest educational qualification* moderates the effect of *labelling* or *availability* on *energy of the main* (i.e., the *labelling\* highest educational qualification* or *availability\* highest educational qualification* interaction is significant), moderated mediation analyses will be performed in order to examine the extent to which health motivation (HM) (healthiness motivation and weight control motivation) mediates the effect of *highest educational qualification* on *energy of the main* with and without labelling.

If the main analysis reveals any significant interactions between *labelling* or *availability* and *familiarity*, then repeated ordering will be aggregated at participant level by calculating the average energy of the mains for familiar and unfamiliar cuisines separately. If the main analysis reveals no interaction between *labelling* or *availability* and *familiarity*, then repeated ordering will be aggregated at participant level by calculating the average energy of the mains for all cuisines.

Conceptual diagram example (labelling):

Statistical diagram example (labelling):

Conditional indirect effect of *highest educational qualification* on the *average energy of the mains* through *HM* =  $a(b_1 + b_2)$  *labelling*.

The moderated mediation will be tested by estimating the conditional indirect effect of *level of education* on the *energy of the main* through *HM* for *labelling* and *no labelling* conditions (resp. the *increased* and *baseline availability* conditions) and testing the conditional indirect effect for those conditions using bias-corrected bootstrap. We will use the PROCESS macro (Model 15) on SAS version 9.3 that provides asymmetric bias-corrected bootstrap confidence intervals for inference about the conditional indirect effects using 5,000 bootstrap samples [38]. Moderated mediation will be tested by determining whether or not the confidence intervals contain zero.

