## **19. APPENDIX K: DEBRIEFING TEXT**

*"In this study we were interested in the effect of nutrition interventions on food choices at restaurants.*

*All the participants saw the same six dining out scenario but in four different conditions. In the first condition, the menus reflected the food offer that can be found in restaurants in the US – for the six specific cuisines; in the second one energy labels for each food item were added on the menus; in the third one the proportion of healthy food items (low energy) was increased; in the fourth one energy labels were added and the proportion of healthy food items was increased. We will compare the total energy of the food items selected by the participants from the four conditions. The results will help to identify the most promising intervention to reduce the overall energy when dining out. You saw familiar and unfamiliar restaurants menus because we will test whether the effect of the interventions is influenced by how familiar the menu options are.*

*You also answered questionnaire about your food choices motivations and nutrition knowledge. We will test if the ones who are the most motivated by health in their food choices and who have better nutrition knowledge were more likely to use energy information when making food choices.*

*Thank you very much for your participation in our study!"*

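### The hypothesis that higher-SES participants are more health-motivated has no test of its own; it is examined only inside a mediation analysis that may never be run

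*Combined protocol and SAP*

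**What the plan says.** Section 2 sets a secondary objective: "To examine the reasons why the effects that energy labelling have on kcals ordered may vary based on" participants' SES. The outcome listed beside it is the health-motivation questionnaire score. The hypothesis has two legs: "The participants of higher SES will be more motivated by health in their food choices than participants of lower SES, which will mediate" the link between SES and the label effect.

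Section 7.4 takes the healthiness item (item 1 of the single-item Food Choice Questionnaire) as the measure of health motivation and the lower/higher split of educational qualification as SES. Section 7.5 then makes the only analysis of motivation conditional on a significant interaction of education with labelling or with availability. The operative words are "interaction is significant), moderated mediation analyses will be performed in order to examine the extent to which health motivation (HM".

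Under the Debriefing questionnaire heading of section 7.5, three linear mixed models take labelling, availability, familiarity and education as effects, "to investigate whether the responses differ across experimental conditions and SES". One outcome is kcal influence. No interactions are listed there, whereas section 7.4 writes out each interaction in the main model. Secondary analyses use an alpha of 0.01.

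**The concern.** The first leg of the hypothesis is a claim in its own right: the two education groups differ in health motivation. It is true or false whatever happens to energy ordered. Under the plan it is reached only if an energy interaction is significant, so a stated hypothesis may receive no test although every analysed participant answers the item.

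A smaller matter sits beside it. Section 7.4 justifies education as the SES measure on the ground that college-educated people are more likely to use kcal labels at restaurants. Kcal influence is the one self-report that bears on this. Without a labelling-by-education term, its model cannot separate use of labels from general attention to calories.

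**Working it through.** **1. Where motivation is analysed.** The section 7.1 table is by condition and overall, and does not list motivation. The section 7.4 models, the sensitivity analyses and the debriefing analyses do not use it as outcome or predictor. The conditional mediation in section 7.5 is the only place where it enters.

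**2. How often the condition fails.** Section 7.6 gives power 0.81 for an additional 2% reduction through an education interaction, with N = 1,000 and alpha 0.05. To reproduce it:
- Variance of a participant's mean over six menus: 47,244 + 47,244/6 = 55,118, so SD = 234.8 kcal.
- Cells: 500 per labelling level (equal randomisation, section 6), split 40/60 by education (section 4.1: 10% + 30% in the lower group), giving 200 and 300.
- SE of the interaction: 234.8 × √(2/200 + 2/300) = 30.3 kcal.
- Effect: 2% of 706 = 14.1 kcal. Power = Φ(14.1/30.3 − 1.96) = 0.07, two-sided.

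This closed-form check does not return 0.81. The plan used simulation with settings not fully shown, so that is a separate matter and the point does not rest on it. Treating the two interaction tests as independent, the chance that the mediation is not run is:

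| Situation | Calculation | Not run |
|---|---|---|
| Labelling interaction real at stated power, availability null | 0.19 × 0.95 | 0.18 |
| Both real at stated power | 0.19² | 0.04 |
| Both null | 0.95² | 0.90 |
| Labelling interaction of 2% on the SE above (power 0.075 counting both tails), availability null | 0.925 × 0.95 | 0.88 |

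If a familiarity interaction triggers the stratified models of section 7.4, these may give further chances to meet the condition. They are not counted here.

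**3. Power of a direct test of education against motivation.** Inputs: r = 0.17 (section 7.6, from the earlier virtual fast-food trial), N = 1,000, alpha 0.01 two-sided. Power = Φ(atanh(r) × √997 − 2.576).
- r = 0.17: 0.1717 × 31.58 − 2.576 = 2.85, power 0.998.
- Dichotomising education weakens r. With the section 4.1 percentages and the advanced-degree 10% divided equally between codes 5 and 6 (assumption), the binary split correlates 0.79 with the ordinal score. Then r ≈ 0.17 × 0.79 = 0.134 and power is 0.95. Other divisions of that 10% give correlations of 0.76 to 0.83 and power of 0.94 to 0.97.
- If the true r were only 0.10 (assumption), power would be 0.72, or 0.47 after the split.

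**4. The kcal-influence model.** If the education groups differ by d only when labels are shown, equal allocation makes the main-effects estimate (d + 0)/2 = d/2, and nothing in the model attributes it to labels. For the added interaction:
- SE = SD × √(2/200 + 2/300) = 0.129 SD. For an assumed SD of 1.5 to 2.0 on the 7-point item, this is 0.19 to 0.26 points.
- Detectable with 80% power at 0.01: (2.576 + 0.842) × 0.129 = 0.44 SD, or 0.66 to 0.88 points.
- Power at smaller interactions: 0.15 at 0.2 SD, 0.40 at 0.3 SD.

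**5. Familiarity.** In Appendix J the calorie item is asked once, not per cuisine. Each participant supplies one value, so a within-subject familiarity effect cannot be estimated for it.

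**The case against.** The condition has a rationale. If label effects do not vary by SES, there is nothing for the mediation to explain, and if the condition is met the education-to-motivation path is estimated anyway. That stands for the mediation. It does not cover the plain comparison of motivation by education, which does not depend on any energy interaction.

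A direct test also shows only that the groups differ. It does not link motivation to the label effect, and section 7.6 already reports r = 0.17 from an earlier trial. This too stands: the remedy tests the first leg and no more.

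A reader might infer that the missing labelling-by-education term leaves the whole objective unanswered. The documents do not support that. Section 2 names health motivation, not kcal influence, as the outcome for this objective and ties kcal influence to none. The debriefing analysis is introduced as exploratory, and its stated purpose is met by main effects. The Appendix J item asks about calories the participant thought were in the food, so people who saw no labels can agree with it. It is not a pure measure of label use.

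A reader might also take the debriefing text in Appendix K, which says the study will test who "were more likely to use energy information when making food choices", as a promise of this interaction. That sentence concerns health motivation and nutrition knowledge and does not mention education.

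**Conclusion.** The point holds for the motivation hypothesis. Section 2 states it and names its outcome, and section 7 offers no test that is sure to be run. On the plan's own power figure, the comparison is skipped about 18% of the time when only the labelling interaction is real, and about 90% of the time when neither is. These figures assume independent tests. A direct test would be well powered (about 0.95 to 0.998) if r = 0.17 carries over to this sample, and less so if the correlation is nearer 0.10.

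The kcal-influence term is a useful exploratory extra. It has 80% power only for about 0.44 SD under a 40/60 education split, so a non-significant result would say little. Neither addition would by itself explain why label effects differ by SES.

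**What to change.** In section 7.5, pre-specify one linear model with healthiness motivation (item 1) as outcome and highest educational qualification (lower vs. higher) as predictor. Adjust it for labelling and availability, because section 6 places the questionnaire after the meal task. Test at 0.01, report the difference with its interval, and run it whatever the main analysis shows. State that it addresses the first leg of the hypothesis only. The mediation may stay conditional.

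As a lesser addition, include labelling-by-education in the kcal-influence model and report the education difference with and without labels as estimates with intervals. Drop familiarity from that model, which leaves one record per participant and an ordinary linear model. Align the item number as well: section 7.2 calls it item 3, Appendix J item 2.

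The cost is one or two more tests at 0.01 and no new data. Both lines need to be in place before results are seen; added later, they would be post hoc.
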